3. ENDPOINTS AND BASELINE VARIABLES: DEFINITIONS AND CONVENTIONS

3.1. Primary Endpoint

Loss of response requiring rescue treatment will be evaluated in each group during the blinded treatment period. Loss of response is denoted as a flare and is defined as a loss of at least 50% of the Eczema Area and Severity Index (EASI) response at Week 12 and an Investigator's Global Assessment (IGA) score of 2 or higher.

Detailed descriptions of how the IGA and the EASI scores are derived are provided in [Appendix 3](#) and [Appendix 4](#) respectively.

Calculation for determining flare:

If x_0 is the EASI score at baseline and x_R is the EASI score at Week 12 (randomization), the EASI response at Week 12 (randomization) is defined as $x_R - x_0$. During the randomized, double-blind period, a subject would have met the definition of a flare if their EASI score is greater than or equal to $x_R + 0.5 \times |x_R - x_0|$ and their IGA score is greater than or equal to 2.

For example, if a subject has a total EASI score of 40 at baseline and a score of 10 at Week 12 (achieving EASI-75 to be a responder at randomization), the EASI response is -30. To meet the definition of flare, the total EASI score for this subject would have to go up by at least 15 (50% of -30) from Week 12, which computes to a total EASI score of at least 25, and in addition have an IGA score of ≥ 2 .

3.2. Key Secondary Endpoint

As the key secondary endpoint, loss of response is defined as being no longer able to maintain an IGA score of 0 or 1 (as at randomization) and having an IGA score of ≥ 2 during the randomized, double-blind period.

3.3. Secondary Endpoints

A list of all the secondary and other endpoints is already provided alongside the study objectives in [Table 2](#). Here we describe definitions for some of the clinical efficacy endpoints.

3.3.1. Response Based on the IGA Score

A successful response at a visit (eg, Week 12) is defined as an IGA score of 0 (clear) or 1 (almost clear) and a drop of ≥ 2 points in the IGA score from baseline (see [Section 3.4](#) for definitions of baseline).

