#### **Clinical Efficacy Assessments in Subjects Requiring Rescue Treatment:**

1. Response based on the IGA at the end of rescue therapy.
2. Response based on the EASI total score at the end of rescue therapy.
3. Response based on achieving  $\geq 4$  point improvement in the severity of pruritus Numerical Rating Scale (NRS) at the end of rescue therapy relative to the start of rescue therapy baseline value.
4. Percent change in percent Body Surface Area (BSA) at the end of rescue therapy relative to the start of rescue therapy baseline value.
5. Percent change in SCORAD subjective assessments of itch and sleep loss at the end of rescue therapy relative to the start of rescue therapy baseline value.
6. Response based on achieving a  $\geq 50\%$  and  $\geq 75\%$  improvement in SCORAD (SCORAD-50, SCORAD-75) at the end of rescue therapy relative to the start of rescue therapy baseline value.

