### **9.2.4. Analysis of Secondary Endpoints**

In general, binary endpoints (such as EASI-50, EASI-90 or the proportion of subjects achieving  $\geq 4$  point improvement in severity of pruritus NRS measure) will be analyzed using the (Cochran-Mantel-Haenszel) test adjusted by randomization strata (age groups) and baseline disease severity. The difference between treatment groups in the proportion of subjects achieving a response along with its 95% confidence interval (using the normal approximation for the difference in binomial proportions) will be reported. If a subject withdraws from the study, then this subject will be counted as a non-responder for endpoints

after withdrawal. In addition, a subject in the FAS-RA subset who receives rescue treatment due to protocol-defined flare will be considered a non-responder.

For continuous endpoints, such as percent change from baseline in the EASI total score and BSA or change from baseline in SCORAD, PSAAD, DLQI/CDLQI, POEM, HADS, and change from baseline in the pruritus severity using the NRS measure, a mixed-effect model with repeated measures (MMRM) will be used. This model will include the factors (fixed effects) for treatment group, randomization strata (age groups), and baseline disease severity, visit, treatment-by-visit interaction, and relevant baseline value. Within the framework of MMRM, differences between groups will be tested using estimates from the MMRM model.

For all binary endpoints, missing data will be handled by considering subjects who withdraw or randomized subjects receiving rescue treatment as non-responders. No imputations will be made for continuous data and missing data will be considered to be MAR.

In general all secondary endpoints will be analysed for the FAS-RA subset. For the subjects requiring rescue therapy (FAS-RE subset), the response achieved at the end of the rescue period will be assessed in relation to the start of the rescue period. In addition to these two analysis sets, secondary endpoints will also be summarized for all subjects participating in the open-label run-in period (FAS-OL subset).

Hypotheses for all relevant secondary endpoints will be tested at the nominal 5% level of significance, without adjustments for multiple comparisons.

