2.2. Study Design

This is a randomized, responder-enriched, double-blind, placebo-controlled, Phase 3 withdrawal trial to evaluate the efficacy and safety of PF-04965842 monotherapy in subjects aged 12 years and older with chronic moderate to severe AD as defined per the inclusion criteria and a body weight ≥ 40 kg.

The trial consists of an open-label run-in period to determine responder status to an initial induction treatment with 200 mg PF-04965842 QD, a randomized, placebo-controlled, double-blinded PF-04965842 maintenance treatment period, and a 4-week untreated follow-up safety period. A study design schematic is presented in [Figure 1](#).

Figure 1. Study Design Schematic

Note: Flare is defined as a loss of response associated with a decrease of at least 50% of the EASI response compared to randomization and an IGA score of ≥ 2 .

Responder criteria are defined as a) achieving an IGA of clear (0) or almost clear (1) (on a 5-point scale), b) a reduction from IGA baseline of ≥ 2 points, and c) reaching an EASI-75 response (at least 75% improvement). Subjects not meeting criteria are declared as non-responders and are not eligible for randomization in this study. They may choose to enroll into the PF-04965842 Long Term Extension (LTE) study B7451015 providing they remain eligible; otherwise, they are permanently discontinued from treatment and enter the 4-week untreated follow-up period in this study.

Responders at the end of the 12-week open-label run-in period enter the 40 week, double-blind, maintenance treatment period in which they are randomized 1:1:1 into either PF-04965842 200 mg QD, PF-04965842 100 mg QD or placebo. Randomization is stratified by age category, ie, <18 years and ≥ 18 years.

Following completion of the 40-weeks of blinded treatment, all subjects are to be assessed for eligibility to enter study B7451015. If a subject discontinues prematurely or is not eligible/willing to participate in B7451015, then the subject enters the 4-week untreated follow-up period.

During the blinded treatment period, subjects meeting the protocol definition of flare enter an open-label rescue period during which they receive another 12-week course of PF-04965842 200 mg QD with topical therapy per local standard of care (SOC). In this study, flare

requiring rescue treatment will be defined as a loss of at least 50% of the EASI response at Week 12 and an IGA score of 2 or higher.

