4.1. Full Analysis Set (FAS)

The following groups of FAS will be defined for this study:

FAS-OL: This is the set of all subjects who received at least one dose of study treatment during the open label run-in phase. For all analyses, Study Baseline will be used (see [Section 3.4](#)).

FAS-RA: This is the set of all subjects who have been randomized at Week 12 and have received at least one dose of study treatment within the double-blind phase. By study design, this will be a subset of FAS-OL. Subjects are assigned to the randomized treatment group regardless of actual treatment received. All analyses will be reported by treatment

regimen/sequence (eg, OL 200 mg → DB 200 mg or OL 200 mg → DB 100 mg or OL 200 mg → DB Placebo). For analysis purposes, either the Study Baseline or the Randomization Baseline will be used, depending on the endpoint and/or the analysis (see [Sections 3.4 and 6](#)).

FAS-RE: This is the set of all subjects who have met the protocol definition of a flare (see [Section 2.2](#)) during the double-blind phase and have received at least one dose of rescue treatment. By study design, this will be a subset of FAS-RA. In general, for efficacy analyses, Rescue Baseline will be used (see [Section 3.4](#)).

In general, change from baseline analyses based on any of the above FAS groups will require at least one post-baseline observation recorded. Analyses for endpoints that are defined based on a threshold of change from baseline (eg, NRS4) will also require the baseline value to meet that threshold (eg, for NRS4, the baseline value needs to be ≥ 4).

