6.3. Secondary Endpoints (Efficacy)

6.3.1. Response Based on (IGA, EASI-50, EASI-75, EASI-90, EASI-100, NRS4 for Severity of Pruritus, SCORAD50 and SCORAD75, IGA + EASI-75)

	All Randomized Subjects	Randomized Subjects Requiring Rescue Treatment	Pre- Randomization Subjects
Summary	Proportion of subjects achieving a response at Weeks 12, 16, 28, 40 and 52	Proportion of subjects achieving a response at Rescue Weeks 2, 4, 8 and 12	Proportion of subjects achieving a response at Weeks 2, 4, 8 and 12
Population	FAS-RA	FAS-RE	FAS-OL
Baseline	Study (see Section 3.4)	Rescue (see Section 3.4)	Study (see Section 3.4)
Statistical Method	CMH and normal approximation as in Section 5.2.1 .	Normal approximation as in Section 5.2.1 .	Normal approximation as in Section 5.2.1 .
Missing Data	Missing values after dropout are defined as “non-response” (see Section 5.3.1)	Missing values after dropout are defined as “non-response” (see Section 5.3.1)	Missing values after dropout are defined as “non-response” (see Section 5.3.1)

6.3.2. Change from Baseline in (Total EASI Score, SCORAD (VAS) Pruritus and Sleep Sub-Scales, PP-NRS for Severity and Percent BSA)

	All Randomized Subjects	Randomized Subjects Requiring Rescue Treatment
Summary	Change from baseline at Weeks 12, 16, 28, 40 and 52	Percent change/Change from baseline at Rescue Weeks 2, 4, 8 and 12
Population	FAS-RA	FAS-RE
Baseline	Study (for Week 12); Randomization (for visits after Week 12) (see Section 3.4)	Rescue (see Section 3.4)
Statistical Method	MMRM as in Section 5.2.2	MMRM as in Section 5.2.2
Missing Data	Use observed data (see Section 5.3.2)	

Change from Study Baseline at Week 12 and its 95% CI will be estimated for each randomized treatment group using an MMRM analysis using data from Weeks 2, 4, 8 and 12. For PP-NRS, data will be included from Days 2 – 15, Weeks 4, 8 and 12.

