9. APPENDICES

Appendix 1. Summary of Clinical Efficacy Analyses

Clinical Efficacy Endpoints	Analysis Set	Baseline	Analysis Method	Missing Data Imputation	Primary Analysis for Primary Endpoint
Loss of Response	FAS-RA	Randomization Date	Time to Event	CAR	Yes
Loss of Response	PPAS	Randomization Date	Time to Event	CAR	No
Loss of Response	FAS-RA	Randomization Date	Time to Event	CNAR	No
Loss of Response based on the IGA score	FAS-RA	Randomization Date	Time to Event	CAR	
Loss of Response based on the IGA score	PPAS	Randomization Date	Time to Event	CAR	
Weeks 2, 4, 8 and 12 IGA Response	FAS-OL	Study	Normal approx.	NR	
Weeks 12, 16, 28, 40 and 52 IGA Response	FAS-RA	Study	CMH and Normal approx.	NR	
Rescue Weeks 2, 4, 8 and 12 IGA Response	FAS-RE	Study	Normal approx.	NR	
Weeks 12, 16, 28, 40 and 52 EASI-50 Response	FAS-RA	Study	CMH and Normal approx.	NR	
Weeks 2, 4, 8 and 12 EASI-75 Response	FAS-OL	Study	Normal approx.	NR	
Weeks 12, 16, 28, 40 and 52 EASI-75 Response	FAS-RA	Study	CMH and Normal approx.	NR	
Rescue Weeks 2, 4, 8 and 12 EASI-75 Response	FAS-RE	Study	Normal approx.	NR	
Weeks 12, 16, 28, 40 and 52 EASI-90 Response	FAS-RA	Study	CMH and Normal approx.	NR	
Weeks 2, 4, 8 and 12 NRS4 Severity Response	FAS-OL	Study	Normal approx.	NR	
Weeks 12, 16, 28, 40 and 52 NRS4 Severity Response	FAS-RA	Study	CMH and Normal approx.	NR	
Rescue Weeks 2, 4, 8 and 12 NRS4 Severity Response	FAS-RE	Study	Normal approx.	NR	
Weeks 12, 16, 28, 40 and 52 SCORAD50 Response	FAS-RA	Study	CMH and Normal approx.	NR	
Rescue Weeks 2, 4, 8 and 12 SCORAD50 Response	FAS-RE	Study	Normal approx.	NR	
Weeks 12, 16, 28, 40 and 52 SCORAD75 Response	FAS-RA	Study	CMH and Normal approx.	NR	
Rescue Weeks 2, 4, 8 and 12 SCORAD75 Response	FAS-RE	Study	Normal approx.	NR	
Weeks 12, 16, 28, 40 and 52 CFBL in Total EASI Score	FAS-RA	Randomization	MMRM	OD	
Rescue Weeks 2, 4, 8 and 12 PCFBL in Total EASI Score	FAS-RE	Rescue	MMRM	OD	
Weeks 12, 16, 28, 40 and 52 CFBL in Total SCORAD Score	FAS-RA	Randomization	MMRM	OD	
Rescue Weeks 2, 4, 8 and 12 PCFBL in Total SCORAD Score	FAS-RE	Rescue	MMRM	OD	
Weeks 12, 16, 28, 40 and 52 CFBL in NRS Score for Severity	FAS-RA	Randomization	MMRM	OD	
Rescue Weeks 2, 4, 8 and 12 CFBL in NRS Score for Severity	FAS-RE	Rescue	MMRM	OD	
Weeks 12, 16, 28, 40 and 52 CFBL in Percent BSA	FAS-RA	Randomization	MMRM	OD	
Rescue Weeks 2, 4, 8 and 12 PCFBL in Percent BSA	FAS-RE	Rescue	MMRM	OD	

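### SAP 6.3.1 and Appendix 1 give different baselines for the rescue IGA response, and on Rescue Baseline a subject who flares at IGA 2 can respond only by reaching IGA 0

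*SAP*

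**What the plan says.** **Responder rule.** SAP 3.3.1: IGA response "is defined as an IGA score of 0 (clear) or 1 (almost clear) and a drop of" 2 or more points from baseline. It refers to SAP 3.4, which defines a Study, a Randomization and a Rescue Baseline.

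**Entry to rescue.** SAP 2.2 defines flare as "a loss of at least 50% of the EASI response at Week 12 and an IGA score of 2 or higher". Entry at IGA 2 is therefore allowed.

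**Baseline for the rescue response.**
- SAP 6.3.1, whose title lists IGA and IGA + EASI-75, reports for FAS-RE the "Proportion of subjects achieving a response at Rescue Weeks 2, 4, 8 and 12" and gives the baseline as "Rescue (see Section 3.4)".
- SAP 4.1 on FAS-RE: "In general, for efficacy analyses, Rescue Baseline will be used".
- Protocol 9.2.4 on FAS-RE: "the response achieved at the end of the rescue period will be assessed in relation to the start of the rescue period".
- SAP Appendix 1, row "Rescue Weeks 2, 4, 8 and 12 IGA Response", analysis set FAS-RE: the baseline column reads Study.

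**Protocol endpoint.** The rescue list in the Protocol Summary has "Response based on the IGA at the end of rescue therapy", with no baseline and no point drop.

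**The concern.** The 2-point rule is harmless at study entry. Inclusion requires IGA 3 or more, so any fall to 0 or 1 already meets it. Moved to the start of rescue, where IGA 2 is permitted, it begins to exclude people. A subject who flares at IGA 2 and returns to 1 (almost clear) is a failure, while one who flares at IGA 3 and reaches the same score is a success. The milder flare faces the harder test.

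The trial's own benchmark for being in response is IGA 0/1. It is part of the randomization criteria, and losing it is the key secondary endpoint (SAP 3.2). Under 6.3.1 a subject can lose that state, regain it, and still be scored a non-responder.

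Assessing rescue treatment is a declared secondary objective and this is one of its listed endpoints. As the SAP stands, two programmers following different sections would produce different rates.

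**Working it through.** **1. Which final IGA scores count.** The rule is: score at most 1, and baseline minus score at least 2. Study Baseline IGA is 3 or 4 (inclusion criterion 3; severity categories in SAP 5.2.1). Rescue Baseline IGA is 2, 3 or 4 (flare definition).

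| Baseline IGA | Scores counted as response |
|---|---|
| 2 | 0 only |
| 3 | 0 or 1 |
| 4 | 0 or 1 |

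Under Appendix 1 (Study) only the last two rows occur, so the drop never binds once IGA is 0 or 1. Under 6.3.1 (Rescue) all three occur.

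**2. Can a flare happen at IGA 2?** SAP 3.1 sets the EASI threshold at x_R + 0.5 × |x_R − x_0|, where x_0 is the baseline score and x_R the Week 12 score.
- The plan's own example reproduces: 10 + 0.5 × 30 = 25.
- At the minimum eligible baseline of 16, EASI-75 needs x_R of 4 or less. The threshold is then 0 + 0.5 × 16 = 8 (x_R = 0) up to 4 + 0.5 × 12 = 10 (x_R = 4).
- With all four signs mild in every region and a common area score A, EASI = 4 × A × (0.1 + 0.2 + 0.3 + 0.4) = 4A. That is 8 at A = 2, 12 at A = 3, and at most 24 at A = 6.

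A flare with uniformly mild signs is thus feasible at low baselines. It would not reach the threshold of 25 in the plan's example. This shows that IGA 2 entry can occur, not how often.

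**3. Who is in the denominator.** SAP 4.1 requires the baseline to meet the change threshold; its example is a pruritus NRS of 4 or more for a 4-point response. By analogy IGA 2 meets a 2-point threshold, so these subjects stay in and can be counted as failures. The footnote to SAP 6.4.2, placed under PtGA but worded generally, requires a baseline above the threshold. Read literally, it would remove IGA 2 entrants. The rate would then not be lowered, but it would describe only subjects entering at IGA 3 or 4.

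**4. Size if 6.3.1 is followed and IGA 2 entrants are counted.**

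Shortfall = f × p1, where f is the share entering rescue at IGA 2 and p1 the share of those ending at exactly IGA 1.

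Check with assumed values: f = 0.25, and 20% ending at 0 and 40% at 1 whatever the entry score. The proportion at 0/1 is 0.60. The Rescue Baseline rate is 0.75 × 0.60 + 0.25 × 0.20 = 0.50. The difference is 0.10 = 0.25 × 0.40.

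For a range, write p1 = r × q, with r the probability of regaining 0/1 and q the share of those at exactly 1. All values are assumptions.

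| f | r = q = 0.40 | r = q = 0.70 |
|---|---|---|
| 0.10 | 1.6 points | 4.9 points |
| 0.30 | 4.8 points | 14.7 points |
| 0.60 | 9.6 points | 29.4 points |

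**5. Can one baseline serve every rescue response?** Appendix 1 also puts the rescue EASI-75, NRS4 and SCORAD responses on Study baseline, but the protocol words the rescue NRS and SCORAD endpoints relative to the start of rescue. Aligning every row to Study would contradict the protocol. Aligning every row to Rescue creates the IGA problem. Appendix 1 has no rescue row for IGA + EASI-75, so there 6.3.1 alone applies. IGA needs its own decision.

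**The case against.** The strongest reply is that nothing is understated until the baseline is settled. Appendix 1 lists Study for this very endpoint, and under it the problem vanishes. That stands. A reader might infer from 6.3.1 that the rescue rate will certainly be too low, but the documents support only a conditional statement.

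A reader might also infer that the protocol rules out a drop measured from rescue entry, since it ties the NRS, BSA and SCORAD rescue endpoints to the start of rescue but not the IGA endpoint. That does not hold. The rescue EASI endpoint is worded just as barely, and protocol 9.2.4 relates FAS-RE response generally to the start of rescue.

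Third, the PtGA endpoint uses the same 0/1-plus-2-points rule in subjects with a baseline of 2 or more, so a PtGA of 2 must also reach 0. The sponsor has accepted this structure elsewhere, and no document defines the rescue endpoint as regaining IGA 0/1. This shows that the rule could be deliberate. It does not resolve the contradiction between 6.3.1 and Appendix 1, nor make the criterion uniform across entry scores.

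Finally, rescue is open-label with added topical therapy, and counting a fall from 2 to 1 accepts a 1-point change. That is a fair cost of the fix.

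**Conclusion.** Wrong as written. SAP 6.3.1 and Appendix 1 contradict each other on the baseline for the FAS-RE IGA response, and the choice changes who counts as a responder. Most of the text (6.3.1, 4.1, protocol 9.2.4) points to Rescue Baseline, where the 2-point rule sets one success criterion for IGA 2 entrants and another for the rest.

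If 6.3.1 is followed, the reported rate lies below the proportion regaining IGA 0/1 by the share entering at IGA 2 and kept in the denominator, times the share of those ending at exactly 1. Neither share is documented, so the size is unknown. The 2 to 29 points above only illustrate assumed inputs, and no narrower figure is supported.

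The impact is limited. FAS-RE results are single-group proportions with no treatment comparison (SAP 5.2) and lie outside the six-hypothesis sequence (SAP 5.1). The primary and key secondary tests are unaffected.

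**What to change.** - Reconcile SAP 6.3.1 and Appendix 1 before unblinding. State in 3.3.1 and 6.3.1 that, for FAS-RE, IGA response (and the IGA part of IGA + EASI-75) is an IGA of 0 or 1 at the visit. This gives the same IGA result as the Appendix 1 row, because Study Baseline IGA is 3 or 4. It is also always an improvement from rescue entry, because every FAS-RE subject flared at IGA 2 or higher, so it respects protocol 9.2.4.
- Show the Rescue Baseline 2-point version as supportive, in subjects with Rescue Baseline IGA of 3 or higher.
- Keep the rescue EASI, NRS and SCORAD responses on Rescue Baseline as in 6.3.1, and correct their Appendix 1 rows.
- Make the SAP 4.1 text and the 6.4.2 footnote agree on whether a baseline equal to the threshold is included.

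The cost is a few sentences, corrected table entries and one supportive row, with no new data. The downside is that the main rescue rate counts a 1-point improvement as response for IGA 2 entrants; the supportive row keeps the stricter rule visible.

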3.3.2. Responses Based on the Total EASI Score

A successful response on the EASI-50 at a visit (eg, Week 12) is defined as a $\geq 50\%$ improvement in the total EASI score from baseline. Successful responses on the EASI-75, EASI-90 and EASI-100 are defined similarly (with a $\geq 75\%$, $\geq 90\%$ and 100% improvement, respectively).

3.3.3. Response Based on IGA and EASI-75

A successful response (at a given visit) based on both IGA and EASI-75 (IGA + EASI-75) is defined as being a responder on both the IGA (see [Section 3.3.1](#)) and the EASI-75 (see [Section 3.3.2](#)).

3.3.4. Responses Based on the Total SCORAD Score

A detailed description of the derivation of the SCORAD score is provided in [Appendix 5](#). A successful response on the SCORAD-50 at a visit (eg, Week 12) is defined as a $\geq 50\%$ improvement in the total SCORAD score from baseline. A successful response on the SCORAD-75 is defined similarly (with a $\geq 75\%$ improvement).

3.3.5. Response Based on the PtGA Score

A successful response at a visit (eg, Week 12) is defined as a PtGA score of 0 (clear) or 1 (almost clear) and a drop of ≥ 2 points in the PtGA score from baseline.

3.4. Baseline Variables

Baseline values for demographics, medical history, primary diagnosis and prior drug treatments for atopic dermatitis will be based on measures collected at Visit 1/Screening visit or Day 1 visit. For analysis purposes, randomization strata information will be taken from the Case Report Form (CRF).

For all other analyses (including change from baseline), there are three possible choices for baseline in this study as,

Study Baseline: This baseline value will be defined as the last observation collected on or prior to Day 1 (first dose day) of study treatment. If a value is missing on Day 1, then the last available observation before Day 1 will be used. For the PSAAD score, baseline will be defined as a simple average of all values recorded between Day -6 and Day 1.

Randomization Baseline: This baseline value will be defined as the last observation collected between last dose of run-in treatment and Day 1 (first dose day) of randomized treatment. For the PSAAD score, randomization baseline will be defined as a simple average of all values recorded between last dose of run-in treatment and Day 1 of randomized treatment.

Rescue Baseline: This baseline value will be defined as the last observation collected between last dose of blinded treatment and Day 1 (first dose day) of rescue treatment. For the PSAAD score, rescue baseline will be defined as a simple average of all values recorded between last dose of blinded treatment and Day 1 of rescue treatment.

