### **5. STUDY TREATMENTS**

For this study, the investigational products are PF-04965842 and placebo. Enrolled subjects receive 12 weeks induction treatment of 200 mg PF-04965842 QD during an open-label run-in period. At the end of the 12 weeks, subjects responding to treatment as described in [Section 3](#) are randomized into the double-blinded, maintenance treatment period during which they receive 200 mg PF-04965842 QD, 100 mg PF-04965842 QD, or placebo (1:1:1 randomization ratio) for 40-weeks. The last dose of open label run-in treatment (200 mg) is administered at the Week 12 visit; subjects initiate administration of randomized blinded treatment the day after the Week 12 visit. In the event of loss of response during blinded treatment denoted as flare, defined as a loss of at least 50% of the EASI response at Week 12 and an IGA score of 2 or higher, subjects will enter a 12-week open-label rescue period and receive 200 mg PF-04965842 QD with concomitant topical therapy per SOC.

An investigator can temporarily interrupt dosing for up to a maximum of 28 consecutive days for a subject for safety reasons or while monitoring abnormal laboratory tests if the investigator judges that this is necessary ([Appendix 4](#)). The investigator should use their judgement with regard to unscheduled visits/laboratory/clinical assessments required to monitor the subject during this time-frame. If within this timeframe the investigator judges that it is safe to restart dosing, then the subject may restart investigational product. If the

investigator judges that it is not safe to restart dosing within this timeframe, then the subject must be permanently discontinued from treatment, have an End of Treatment visit and enter the 4-week follow-up period. Doses not taken for the reasons mentioned above do not constitute protocol deviations or medication errors and should not be considered dosing errors, but should be noted in the dosing log with the reason for reduced drug consumption clearly described.

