### **5.2. Rescue Treatment**

Subjects will be instructed to contact the site if they experience a significant worsening of their atopic dermatitis, such as a recurrence of pruritus, during the double-blind treatment period. Site staff will determine if the subject should return to the site for an unscheduled (see [Section 6.5.1](#)) or regularly scheduled visit (see [Section 6.3](#)). Subject will be reminded not to take study drug on the day of the site visit. At the visit (regular or unplanned) the subject will be assessed for flare, defined as a loss of at least 50% of the EASI response at Week 12 and an IGA of 2 or higher. Subjects who meet the definition of flare are to receive rescue treatment that day and enter an open-label rescue period during which they receive 12-weeks of 200 mg PF-04965842 QD with concomitant topical therapy per SOC. See [Section 5.2.1](#) for guidance on topical therapies.

After completing the rescue period, subjects are allowed to enter the LTE study B7451015, if eligible. If a subject discontinues prematurely or is not eligible or willing to participate in B7451015, then the subject enters the 4-week, untreated follow-up safety period. Refer to [Schedule of Activities for Rescue Treatment](#).

Subjects not meeting the definition of flare will continue on their blinded treatment. Physicians may continue to clinically evaluate for flare using the EASI and IGA assessments at their discretion.

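### The PSAAD Randomization Baseline averages about two diary days where the Study Baseline averages seven, which gives up some precision in the Week 16 to 52 comparisons

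*SAP*

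**What the plan says.** SAP 3.4 sets a different PSAAD window for each baseline. For the Study Baseline, "For the PSAAD score, baseline will be defined as a simple average of all values recorded between Day -6 and Day 1". For the Randomization Baseline, the PSAAD "randomization baseline will be defined as a simple average of all values recorded between last dose of run-in treatment and Day 1" of randomized treatment. No reason is given for the difference. SAP 3.4 provides a fallback to the last earlier value only under the Study Baseline. The baseline rules in SAP Appendix 2 for the run-in and blinded phases likewise refer only to study Day 1 and the start of study dosing.

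Protocol Section 5 fixes the dates: "The last dose of open label run-in treatment (200 mg) is administered at the Week 12 visit", and "subjects initiate administration of randomized blinded treatment the day after the Week 12 visit". The PSAAD footnote to the Schedule of Activities asks for one entry a day, made before dosing, from screening through End of Study, in selected countries only.

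SAP 6.4.1 analyses PSAAD in FAS-RA by MMRM. It uses the Study Baseline for Week 12 and the Randomization Baseline for Weeks 16, 28, 40 and 52. SAP 5.2.2 puts the baseline value in the model as a covariate. Under SAP 5.1, PSAAD lies outside the testing hierarchy and is tested at a nominal 5%.

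**The concern.** A mean of one or two daily diary values is a less reliable measure of a subject's state than a mean of seven. A less reliable covariate explains less of the follow-up variance and leaves a larger standard error for the treatment difference. Here the loss is avoidable, because the preceding week's entries exist for every subject who kept the diary. It reaches 12 planned comparisons (four visits by three pairwise contrasts).

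The narrow window also leaves little room for missed entries. If nothing was recorded on those one or two days, the SAP gives no way to obtain a baseline. Without one, the subject has no change score and no covariate value.

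**Working it through.** **Day counts.** SAP Appendix 2 runs from Day -1 straight to Day 1, so Day -6 to Day 1 is six days plus one, or seven entries. The Randomization Baseline runs from the Week 12 visit day to the next day. That is two entries by calendar date. It is one if only entries after the last run-in dose count, because the Week 12 entry precedes that dose. The calendar reading is the natural one. Protocol 7.8 puts the visit's assessments before dosing, so a strict after-dose reading would also exclude the Week 12 visit value of every other endpoint that uses this baseline rule.

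**Model.** The plan states no figure to reproduce. Take a daily score with unit variance, of which a share r is stable within the week and 1 - r is independent day-to-day noise. Let c be the correlation of the stable part between baseline and follow-up. The variance of a k-day mean is V_k = r + (1 - r)/k. With follow-up averaged over f days, the residual variance after adjusting for baseline is proportional to 1 - (c r)^2/(V_k V_f). This is a single-visit ANCOVA approximation to the MMRM. The values of r (0.5 to 0.8) and c (0.5 to 0.7) are assumptions.

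**Largest case, r = 0.5, c = 0.7, seven-day follow-up.** V_7 = 0.5 + 0.5/7 = 0.5714, V_2 = 0.75 and (c r)^2 = 0.1225.
- Seven-day baseline: 1 - 0.1225/(0.5714 x 0.5714) = 0.6248.
- Two-day baseline: 1 - 0.1225/(0.75 x 0.5714) = 0.7142.
- Ratio: 0.7142/0.6248 = 1.143. Its square root is 1.069, so the standard error is 6.9% larger.

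**Smallest case, r = 0.8, c = 0.5, seven-day follow-up.** V_7 = 0.8286, V_2 = 0.9 and (c r)^2 = 0.16.
- Seven-day baseline: 1 - 0.16/(0.8286 x 0.8286) = 0.7669.
- Two-day baseline: 1 - 0.16/(0.9 x 0.8286) = 0.7854.
- Ratio: 1.024. The standard error is 1.2% larger.

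**Residual variance, two-day relative to seven-day baseline:**

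| r | c | Follow-up a 7-day mean | Follow-up a single day |
|---|---|---|---|
| 0.5 | 0.5 | 1.056 | 1.029 |
| 0.5 | 0.7 | 1.143 | 1.065 |
| 0.7 | 0.5 | 1.036 | 1.025 |
| 0.7 | 0.7 | 1.097 | 1.060 |
| 0.8 | 0.5 | 1.024 | 1.019 |
| 0.8 | 0.7 | 1.067 | 1.048 |

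Both follow-up columns are needed. SAP 6.4.1 specifies weekly PSAAD data for Weeks 1 to 12 but no averaging rule for Weeks 16 to 52.

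**Sensitivity.** With c = 0.3 and a seven-day follow-up mean, the two-day excess falls to 0.7 to 1.8%. If the daily noise is autocorrelated (AR(1), 0.5), with c back at 0.5 to 0.7, it is 2.3 to 8.5%. Under the strict one-entry reading with independent noise, it is 5 to 26% with a seven-day follow-up mean and 4 to 12% with a single day.

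**Missing baselines.** If a subject completes each day's entry with probability p, independently (an assumption), the chance of no entry in k days is (1 - p)^k. For p from 0.9 down to 0.7 this is 10 to 30% with one day, 1 to 9% with two days, and at most 0.3^7 = 0.02% with seven.

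**The case against.** **The choice is coherent and the stakes are low.** The window follows the general Randomization Baseline rule in SAP 3.4. PSAAD is an unadjusted secondary outcome collected in selected countries, and no power claim concerns it. All of this stands and limits the point to an optional improvement. It is not a reason to keep the shorter window.

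**The size is assumed.** This also stands. Subjects are selected responders and some are then withdrawn to placebo, so the latent correlation could be below 0.5 and the loss correspondingly smaller.

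**The last run-in week might not be stable.** In Phase 2b at 200 mg, IGA and EASI improved until Weeks 4 and 6 respectively and held through Week 12 (Protocol 1.2.4). That is indirect evidence, since it is not PSAAD, but it supports averaging that week.

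Three stronger readings are tempting, and the documents do not support them.
- *The noise passes in full into the change score.* For an unadjusted change score with a seven-day follow-up mean, the two-day penalty would be about 8 to 40% over the same r and c. But the model includes the baseline as a covariate, so subtracting it leaves the treatment differences unchanged. Only the lost explanatory power counts.
- *The Rescue Baseline has the same fault.* Its window is also short: "Subject will be reminded not to take study drug on the day of the site visit", and "Subjects who meet the definition of flare are to receive rescue treatment that day". But SAP 6.3.2, 6.4.1 and Appendix 1 list no PSAAD analysis in FAS-RE, and SAP 5.2 rules out treatment comparisons there. Averaging the week before a confirmed flare could also mix in days before the worsening, so that change would not be free.
- *The loss is as much as 26%.* That figure needs the one-entry reading and the most unfavourable assumptions together. It is also a variance; the standard error would rise by 12%.

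**Conclusion.** The point holds for the Randomization Baseline only. With uninterrupted dosing it averages about two diary entries against seven, although the daily data exist. The cost is precision in the Week 16, 28, 40 and 52 PSAAD comparisons. There is no bias, because the baseline entries precede the first randomized dose and the arms are randomized.

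On the two-day reading, residual variance is about 2 to 14% higher if follow-up is a seven-day mean (standard error about 1 to 7%), and about 2 to 6.5% higher if follow-up is a single day. A middle case (r = 0.7, c = 0.5, seven-day follow-up mean) gives 3.6% in variance and 1.8% in standard error. These sizes depend on the assumed correlations; the day counts do not. A dosing interruption at the Week 12 boundary would lengthen the window for that subject.

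The gap in the missing-data rule is a separate reason for the change and may matter as much as the variance.

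**What to change.** In SAP 3.4, define the PSAAD Randomization Baseline as the mean of diary entries in the seven days up to and including the pre-dose entry on Day 1 of randomized treatment. State a minimum number of entries for the mean to count. It would also help to say in SAP 6.4.1 how daily PSAAD entries are summarised at Weeks 16 to 52. Leave the Rescue Baseline as it is.

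The cost is a sentence or two in the SAP before unblinding. No new data are needed and no other endpoint changes. A fixed window also settles the one-or-two-entry ambiguity and no longer depends on dosing interruptions. This is a free improvement.
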